For the survey of the programme acceptance, a list of possible candidates (sex and gender balanced) will be made for both groups, health professionals and migrant patients. The same member of the PCC leadership team that sent the invite to the GP and nurses for the FGs of the 6 participating PCCs will send an anonymous questionnaire via email or WhatsApp, using the secured LimeSurvey platform, to the chosen health professionals and migrant patients. Candidates will receive the invitation by email or message with a link to the anonymous survey and their access to it will represent their consent to participate.

6. STUDY PROCEDURES, TREATMENT AND CALENDAR OF THE STUDY.

In line with the existing national guidelines, active TB will be screened with chest radiography. If radiographic findings are compatible with TB, or if TB symptoms are present, the person should be immediately referred to a specialist for full diagnostic workup. For HIV testing, a standard HIV ELISA test will be performed. For HBV, the Australian antigen (HBsAg) and the IgG Core (IgG anti-HBc) serological test will be performed. For HCV, an IgG-HCV test will be performed. For Chagas disease, strongyloidiasis and schistosomiasis, a serological test will also be performed. All of them will be processed in the reference laboratory facility of the PCC, being all of them based on the commercial tests available in each hospital of reference. Finally, for female genital mutilation, a gynaecological physical examination will be performed and/or referral to a gynaecologist will be carried out if required. A preventive protocol will be applied for girls at risk of this practice.

In the case of a positive test result or diagnosis, the individuals will be referred to receive specialized care as appropriate.

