2.3 Endpoints

Primary Endpoints

Endpoint 1: For the detection rate of all aggregated infections, the monthly detection rate based on positive serologies, chest radiographies, the International Classification of Diseases Ninth Revision (ICD-9 for Andalusia) or Tenth Revision (ICD-10 for Catalonia) of FGM and/or gynaecologist referrals will be considered within the migrant patients who visited their assigned centre during the intervention period. Also, positive tuberculin skin test (TST) and/or Interferon Gamma Release Assay (IGRA) and stool samples will be considered for the Andalusian site. Control and intervention PCCs will be compared before and after the implementation.

Secondary Endpoints

Endpoint 2: For the detection rate of each individual condition, the infections and FGM, the monthly detection rate based on positive serologies, chest radiographies, ICD-9/ICD-10 of FGM and/or gynaecologist referrals, TST/IGRA and stool samples (for Andalusia) will be considered within the migrant patients who visited their assigned centre during the intervention period. Control and intervention PCCs will be compared before and after the implementation.

Endpoint 3: The number of early diagnoses of HIV will be assessed using the CD4 cell count of migrant patients diagnosed with an HIV infection, and will be compared between the control

and intervention PCCs before and after the implementation. If possible, we will estimate the monthly detection rate of early HIV diagnoses and also compare it between the intervention and control PCCs.

Endpoint 4: The number of early diagnoses of HBV and HCV will be assessed using the levels of transaminases, platelets, bilirubin, and clotting parameters from blood analyses of migrant patients diagnosed with HBV or HCV, and will be compared between the control and intervention PCCs before and after the implementation. If possible, we will estimate the monthly detection rate of individuals diagnosed with HBV or HCV presenting high levels of transaminases, platelets, bilirubin, and clotting parameters and also compare it between the intervention and control PCCs.

Endpoint 5: The number of the screening tests performed of all aggregated infections (serological tests, chest radiographies, TST or IGRA tests and stool samples in the case of the Andalusian site) will be compared between the intervention and control PCCs before and after the implementation.

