5.4 Interim Analysis and Data Monitoring

No interim analysis will be conducted. However, the Sistema d'Informació dels Serveis d'Atenció Primària (SISAP) will supervise the technical monitoring of the tool in the implementation phase of the study. Simultaneously, aggregated data will be obtained via SIDIAP during the process of implementation of the tool in the Catalan Institute of Health with the sole objective of technical monitoring to identify alert errors and provide subsequent remediation.

6. Data analysis

Since the ISMiHealth tool is in different phases of implementation in each site, and the algorithms are based on different recommendations, there will be two independent data analyses: i) in Catalonia, the health impact of the tool will be evaluated in 35 PCCs; and ii) in Andalusia, the preliminary effectiveness data will be estimated in the six PCCs where the tool will be pilot tested.

The precision for the reporting of the results will be 95%, considering statistically significant p.values<0.05.

First, for the description of the sample and data obtained from the screening program in each study site, summary statistics will be presented as frequencies for categorical variables, as means with standard deviations (SD) for normally distributed continuous variables and medians with interquartile range (IQR) for non-normally distributed continuous variables (Table 1 and 2).

Data analysis in Catalonia

- a. Health impact of the tool. The effectiveness of the tool will be evaluated and compared between the intervention and control centres. Significant deviations between intervention and control centres before the implementation of the screening program will be suggestive of the main underlying assumption, presenting parallel trends prior to implementation.
 - The primary outcome of the study will be the detection rate of the aggregated infections, while the detection of the individual conditions will be considered as secondary outcomes of the study. To analyse the effect of the intervention on the outcomes, difference in differences approach will be performed using a generalized linear model. Intervention and control PCCs will be compared before and after implementation with respect to the monthly detection rate. Standard errors will be clustered at the

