| | FGM (completed | |
| | questionnaires) | |
| Associations with the scre | ening performance for all | Bivariate and multivariate |
| aggregated infections | | analysis |
| | HIV | |
| | Syphilis^ | |
| Associations with the | HBV | Bivariate and multivariate |
| screening performance | HCV | analysis |
| for each individual | active TB | |
| condition | latent TB^ | |
| | T.cruzi infections | |
| | S.stercoralis infections | |
| | Schistosoma spp. infections | |
| | Intestinal parasites^ | |
| | FGM | |
| Patients under follow-up a | after diagnosis | Bivariate analysis |
| Patients under treatment | after diagnosis | Bivariate analysis |
| Cured patients | | Bivariate analysis |
| | HIV | |
| | Syphilis^ | |
| | HBV | Numerator: number of |
| Prevalence of each | HCV | detected cases for each |
| condition | active TB | specific condition. |
| | latent TB^ | Denominator : number of |
| | T.cruzi infections | tested patients for each |
| | S.stercoralis infections | specific condition. |
| | Schistosoma spp. infections | |
| | Intestinal parasites^ | |
| | FGM | |

HIV: human immunodeficiency virus, HBV: hepatitis B virus, HCV: hepatitis C virus, TB: tuberculosis, FGM: female genital mutilation, TST: tuberculin skin test, IGRA: Interferon Gamma Release Assay; ^Only in the Andalusian site; The detection rate of all aggregated infections and the individual conditions will be calculated using the numbers of diagnoses per month over at least five years until the end of the intervention.

Figure 1. Flow chart of the migrant population

Figure 2. Monthly detection rates of the aggregated infections

Figure 3-9. Monthly detections of each individual condition (infections and FGM)

8. Reporting Conventions

Dates will be reported using the format MM/DD/YYYY. P-values will be reported to 3 decimal places. P-values less than 0.001 will be reported as '<0.001'. Statistics such as means, standard deviations, median values and percentages, will be calculated using the same decimal digits as the raw data. Rounding off will be performed on the final calculation value and reported according to publication requirements.

9. Technical Details

The data of the ISMiHealth study will be analysed with Stata Statistical Software: Release 16. At the time of the writing, the operating system of the computer that will be used for the analysis is Windows.

10. Summary of Changes to the Protocol

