| alert_fgm | Patients fulfilling the criteria for the screening of FGM | Qualitative | Yes/No |
| sero_hiv | Serologies for HIV | Qualitative | Yes/No |
| sero_syph^ | Serologies for syphilis | Qualitative | Yes/No |
| sero_hbv | Serologies for HBV | Qualitative | Yes/No |
| sero_hcv | Serologies for HCV | Qualitative | Yes/No |
| cxray | Chest radiographies for active TB | Qualitative | Yes/No |
| tst^ | TST for latent TB | Qualitative | Yes/No |
| igra^ | IGRA for latent TB | Qualitative | Yes/No |
| sero_chagas | Serologies for T.cruzi infection | Qualitative | Yes/No |
| sero_strongy | Serologies for S.stercoralis infection | Qualitative | Yes/No |
| sero_schisto | Serologies for Schistosoma spp. infection | Qualitative | Yes/No |
| stool_intpar^ | Stool samples for intestinal parasites | Qualitative | Yes/No |
| fgm | Questionnaires completed for FGM | Qualitative | Yes/No |
| dx_hiv | Diagnosis of HIV | Qualitative | Yes/No |
| cd4 | CD4 cell count | Quantitative | |
| hiv_vl | HIV viral load | Quantitative | |
| dx_syph^ | Diagnosis of syphilis | Qualitative | Yes/No |
| dx_std | Diagnosis of other sexually transmitted diseases (STDs) | Qualitative | Yes/No |
| dx_hbv | Diagnosis of HBV | Qualitative | Yes/No |
| dx_hcv | Diagnosis of HCV | Qualitative | Yes/No |
| dx_activetb | Diagnosis of active TB | Qualitative | Yes/No |
| dx_latenttb^ | Diagnosis of latent TB | Qualitative | Yes/No |
| dx_chagas | Diagnosis of T.cruzi infection | Qualitative | Yes/No |
| dx_strongy | Diagnosis of S.stercoralis infection | Qualitative | Yes/No |

| dx_schisto | Diagnosis of Schistosoma spp. infection | Qualitative | Yes/No |
|-----------------|--|--------------|---|
| dx_intpar^ | Diagnosis of intestinal parasites | Qualitative | Yes/No |
| dx_fgm | Diagnosis of FGM cases | Qualitative | Yes/No |
| referral | Referral to specialists due to a diagnosis during the intervention | Qualitative | Yes/No |
| other_dx | Other diagnoses made during the intervention (besides from the infections included in the study and FGM) | Qualitative | ICD-9 or ICD-10 |
| com_dx | Comorbidities | Qualitative | ICD-9 or ICD-10 |
| immune_dx | Immunosuppressive diagnoses during the intervention period | Qualitative | ICD-9 or ICD-10 |
| drugs | Drugs prescribed to patients during the intervention | Qualitative | Anatomical Therapeutic Chemical (ACT) codes |

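### FGM detection counts gynaecologist referrals before and after implementation, but the only referral field covers any specialist and only the intervention period

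*SAP*

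**What the plan says.** **Endpoint.** In SAP 2.3, Endpoint 2 (detection of each condition) lists its sources so that "ICD-9/ICD-10 of FGM and/or gynaecologist referrals, TST/IGRA and stool samples (for Andalusia) will be considered". Endpoint 1 carries the same element: ICD codes "of FGM and/or gynaecologist referrals will be considered within the migrant patients who visited their assigned centre during the intervention period". For both, "Control and intervention PCCs will be compared before and after the implementation".

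**Analysis.** SAP Section 6 states: "To analyse the effect of the intervention on the outcomes, difference in differences approach will be performed using a generalized linear model". The footnote to SAP Table 4 says that detection rates "will be calculated using the numbers of diagnoses per month over at least five years until the end of the intervention".

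**Data.** SAP 3.4 and 5.1 make the Annex 1 variables the analysis dataset. Annex 1 has one primary-care referral row, Yes/No: "Referral to specialists due to a diagnosis during the intervention". The FGM row reads "Diagnosis of FGM cases", also Yes/No, with no period limit and no statement that it includes referrals. The other hospital rows describe admissions and visits after an admission, not referrals.

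**Related text.**
- Protocol Section 6: for FGM, "a gynaecological physical examination will be performed and/or referral to a gynaecologist will be carried out if required".
- Protocol Section 7, study variables: FGM codes are taken over the last 10 years; specialist referral is listed with neither a period nor a specialty.
- SAP Section 6(b), on prevalence: FGM cases are taken from completed questionnaires and/or referrals to specialists, again with no specialty named.

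**The concern.** The endpoint needs gynaecologist referrals for FGM, placed in calendar months, before and after implementation. The field specified for extraction gives none of these: no specialty, no date, no earlier period. Two separate problems follow.

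1. **Period.** The FGM case definition widens at the implementation date. SAP Section 6 uses the pre-implementation series to judge parallel trends. That check would run on codes alone, while the effect is estimated on codes and/or referrals.
2. **Specificity.** Protocol Annex 1 (item 12) and Annex 2 (item 13) state that people diagnosed with any of the listed conditions should be referred. A referral flag for any specialist therefore also fires for infections. If it is used for FGM, infection referrals that rise with the tool could be read as FGM detections.

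**Working it through.** The plan states no figure on this point, so there is none to reproduce. The check compares sources by period and then asks what the mismatch does to the estimate.

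**Step 1. Sources available by period (SAP Annex 1)**

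| FGM source | Before implementation | During intervention |
|---|---|---|
| ICD code | yes (no period limit) | yes |
| Referral field | no | yes, any specialist, after a diagnosis |

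The words about the intervention may attach to the referral or to the diagnosis. Either way, referrals belonging to the earlier period are left out.

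**Step 2. Share of the series affected.** Table 4 requires at least five years ending with the intervention, and SAP 3.4 describes a year of intervention. The minimum series is 5 × 12 = 60 months, of which 60 − 12 = 48 have no referral source.

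**Step 3. Effect of the period gap.** Let *s* be the share of FGM detections known only through a referral. The documents give no value, so *s* is assumed. Set the total rate to 1 in both arms, with no true change.

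- Measured before: 1 − s. Measured after: 1.
- Within-arm after/before ratio: 1/(1 − s). For s = 0.10, 0.25 and 0.50 this is 1.11, 1.33 and 2.00.
- Additive difference in differences: [1 − (1 − s_I)] − [1 − (1 − s_C)] = s_I − s_C (true value 0).
- Ratio difference in differences: (1 − s_C)/(1 − s_I) (true value 1).

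| s_I (intervention) | s_C (control) | Additive | Ratio |
|---|---|---|---|
| 0.25 | 0.25 | 0 | 1.00 |
| 0.25 | 0.10 | +0.15 | 0.90/0.75 = 1.20 |
| 0.10 | 0.25 | −0.15 | 0.75/0.90 = 0.83 |
| 0.50 | 0.10 | +0.40 | 0.90/0.50 = 1.80 |
| 0.10 | 0.50 | −0.40 | 0.50/0.90 = 0.56 |

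A real effect survives when the shares are equal. With a true ratio of 1.5, the additive estimate is [1.5 − (1 − s)] − [1 − (1 − s)] = 0.5 for any s, and the ratio estimate is 1.5. With referrals captured alike in both periods, the artefact is zero for any s.

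**Step 4. Effect of non-specificity.** Let *f* be the monthly rate of infection referrals counted as FGM. With the field empty before implementation, the contribution to the additive estimate is f_I − f_C, taken after implementation. If the field were also filled before implementation, the contribution would be (f_I,after − f_I,before) − (f_C,after − f_C,before). That is still positive if the tool raises infection referrals in its own arm. Extending the period alone does not cure this. The documents give no value for *f*.

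**The case against.** **This may be loose wording in one dictionary row.** The protocol lists specialist referral without a period limit, and the Table 4 footnote speaks of diagnoses per month over the full series. Annex 1 is terse throughout: its test and diagnosis rows carry no event dates either. All of this is fair, and the earlier referrals may well exist in the records. But SAP 5.1 makes Annex 1 the dataset, and the period limit on the referral row is explicit where the FGM diagnosis row has none. The FGM row might be meant to combine codes and referrals, but the SAP does not say so.

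**Referrals may add few women.** If the field requires an FGM diagnosis that is already coded, the union of codes and referrals gains nothing and the period gap disappears. That is possible. The endpoint's and/or would then have no function, and referrals made without a code would be missed.

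**Difference in differences cancels the jump.** This largely stands for the period gap. Centres are randomised within pairs (SAP 3.3), so any baseline difference in referral-only detection is a matter of chance, in either direction.

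**Nobody would count an infection referral as FGM.** Endpoints 1 and 2 do say gynaecologist. But the field supplied cannot apply that restriction, and the prevalence rule in SAP Section 6(b) already accepts unspecified specialist referrals for FGM.

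**A stronger reading to avoid.** A reader might compare a codes-only estimate with one that includes referrals and take the gap as the size of the artefact. Suppose codes go from 10 to 12 in the intervention arm and 10 to 10 in control, with 20 and 10 later referrals. The estimate moves from 2 to (12 + 20 − 10) − (10 + 10 − 10) = 12. Restoring equal baseline referrals *r* in both arms gives (12 + 20 − 10 − r) − (10 + 10 − 10 − r) = 12 again. The gap therefore compares two endpoint definitions and does not measure inconsistent capture.

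**Conclusion.** The mismatch is real on the text: Endpoint 2, and Endpoint 1 as worded, cannot be built alike in both periods from the Annex 1 variables. Three consequences follow.

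- **Levels and pre-trend.** Within each arm the apparent before/after ratio is inflated by 1/(1 − s), and the parallel-trends check uses a different case definition from the effect estimate.
- **Difference in differences, period gap.** The bias is zero if referral-only detection is equal between arms at baseline, and of unknown direction otherwise. The ratios of 0.83 and 1.20 rest on assumed shares of 10% and 25%.
- **Difference in differences, specificity.** If the any-specialist field is used for FGM, infection referrals that rise with the tool add to the apparent effect and do not cancel. The size cannot be derived from the documents.

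A reader might infer that the plan builds in a systematic overstatement of the tool's effect. The period gap does not support that, for the reason above. A genuine FGM referral to gynaecology prompted by the tool is also part of the effect that the endpoint defines.

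The scope is mainly a secondary outcome. Within the SAP it reaches the primary only through the wording of Endpoint 1, which conflicts with the infections-only list in Objective 1 (SAP 2.2). Protocol Section 7(d) does list FGM among the aggregated conditions, so that conflict needs settling in its own right.

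**What to change.** 1. Replace the Annex 1 row with a dated, gynaecology-specific, FGM-related referral, extracted in both arms for the whole window before and after implementation. State how codes and referrals combine, counting each woman once.
2. Bring the FGM source in SAP Section 6(b) into line with that definition.
3. If such referrals cannot be extracted for the earlier period, base the FGM difference in differences on the ICD code in both periods and report gynaecology referrals separately as a process measure.

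Cost: extraction is retrospective, so options 1 and 2 are changes to the SAP and the extraction specification, provided that specialty and reason for referral are recorded. Option 3 gives a smaller FGM count and drops a source that the authors chose to include. This matters because Protocol Section 7(g) already expects FGM to be under-ascertained where referral is low.

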- 5. Laboratory or clinical variables: X-rays, serological or microbiology tests for the conditions studied (HIV, HBV, HDC, Chagas disease, strongyloidiasis, and schistosomiasis). In addition, other laboratory parameters will be included (hemogram, including haemoglobin, platelets, leucocytes, neutrophils, lymphocytes, and eosinophils, IgE, liver and renal function creatinine, urea, AST, ALT, GGT, bilirubin, coagulation...)
- 6. Diagnostic variables: Diagnoses of each disease/condition (HIV, HBV, HCV, Chagas disease, strongyloidiasis, schistosomiasis and female genital mutilation) based in ICD 10 codes registered by health professionals in the last 10 years including the intervention period.
- 7. Drug related to the diseases included in the study (e.g., ivermectine for strongyloidiasis) prescribed during the intervention period.
- 8. Co-morbidities: Other diseases diagnoses based on ICD-10 codes registered by health professionals into the system in the last 10 years including the intervention period. The aim is to study the possible association of other diseases (diseases associated with immunosuppression, mental health conditions, cardiovascular and other diseases, other infectious diseases...) with the studied diseases/conditions. In addition, to carry out the cost-effectiveness study (an economic analysis that will be essential to achieve the second objective of the study) all parameters must be considered to adjust the model, including the comorbidities of the diseases.
- 9. Immunosuppression status: Here it will include the prescription and billing of immunosuppressive drugs in the last 10 years including the intervention period as well as ICD-codes on transplant, haematological diseases, cancer and related diagnoses, and autoimmune diseases in the last 10 years for determination of immunosuppression status.
- 10. Minimum basic data set (CMBD) variables: hospitalization dates, primary diagnoses during hospitalizations, laboratory parameters during hospitalizations, drugs prescribed during hospitalization or outpatient units, cost associated or attributed to hospitalization, number of visits in outpatient units

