2.2 Specific Study Objectives

Primary objective 1: To compare the detection rate per month of all aggregated infections (HIV, HBV, HCV, TB, *T.cruzi*, *S.stercoralis* and *Schistosma spp.* infections) between the intervention and control centres over at least five years until the end of the intervention. In the Andalusian site, syphilis, latent TB and intestinal parasites will also be included.

Secondary objective 2: To compare the detection rate per month of each individual condition, the infections and FGM cases, between the intervention and control centres over at least five years until the end of the intervention.

Secondary objective 3: To compare the number of early HIV diagnoses between the intervention and control centres over at least five years until the end of the intervention.

Secondary objective 4: To compare the number of early HBV and HCV diagnoses between the intervention and control centres over at least five years until the end of the intervention.

Secondary objective 5: To compare the number of screening tests performed for all aggregated infections between the intervention and control centres over at least five years until the end of the intervention.

Secondary objective 6: To compare the number of screening tests performed for each individual condition between the intervention and control centres over at least five years until the end of the intervention.

Secondary objective 7: To estimate associations between the screening performance of all aggregated infections with different socio-demographic and epidemiological factors.

Secondary objective 8: To estimate associations between the screening performance of each individual condition with different socio-demographic and epidemiological factors.

Secondary objective 9: To measure the number of the diagnosed individuals with follow-up visits in the hospital of reference.

Secondary objective 10: To measure the number of the diagnosed individuals that have received treatment.

Secondary objective 11: To estimate the prevalence of each infection and FGM in the migrant population.

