3.4 Study Variables

Data will be collected retrospectively, therefore, the data for all the variables mentioned in Annex 1 will be collected after the year of intervention is completed.

4. Sample size calculation

Considering that all PCCs included in the study have a migration density higher than 7%, we have estimated that by including 32 or more centres in Catalonia we will achieve a difference in difference detection rate of all aggregated infections between intervention and control centres of 2, with a 95% precision. A comparative analysis of the PCCs, in relation to the migration density, will be first performed to select the pairs of centres; then, each pair of selected health centres will be randomized, stratifying by study area, using the Statistical software Stata. To assure the validity of results the intervention centres (where the ISMiHealth tool will support the clinicians' decisions) will be compared to the control centres (where the routine care will be followed) with more similar characteristics.

41 PCCs will participate, 35 in the Catalonian site and six in the Andalusian site. In Catalonia 18 PCCs will be intervention and 17 control, not pairing one of the centres; while in Andalusia there will be 3 intervention and 3 control PCCs. The users of the ISMiHealth tool will be the health professionals of the intervention centres and as participants of the study, they will decide whether to follow the recommendations to screen migrant patients, the indirect beneficiaries of the tool. Approximately 980 health professionals will participate in the study.

5. General Considerations

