| immune_drugs | Immunosuppressive drugs prescribed during the intervention period | Qualitative | ACT codes |
| doses | Prescribed drug doses | Quantitative | |
| tto_start | Treatment start date | Quantitative | MM/DD/YYYY: Up to 12/31/2024 |
| tto_end | Treatment end date | Quantitative | MM/DD/YYYY: Up to 12/31/2024 |
| cost | Cost of the prescribed drugs | Quantitative | In euros (€) |
| Hospital (MBDS) | | | |
| hosp | Hospitalisation | Qualitative | Yes/No |
| hosp_dx | Primary diagnosis | Qualitative | ICD9 or ICD-10 |
| hosp_dxother | Other diagnosis | Qualitative | ICD9 or ICD-10 |
| hosp_dates | Hospitalisation dates | Quantitative | MM/DD/YYYY: Up to 12/31/2024 |
| hosp_hgb | Haemoglobin | Quantitative | |
| hosp_plt | Platelets | Quantitative | |
| hosp_wbc | Leucocytes | Quantitative | |
| hosp_neut | Neutrophils | Quantitative | |
| hosp_lym | Lymphocytes | Quantitative | |
| hosp_eos | Eosinophils | Quantitative | |
| hosp_crea | Creatinine | Quantitative | |

| hosp_urea | Urea | Quantitative | |
|-----------------------|--|--------------|---|
| hosp_ast | AST | Quantitative | |
| hosp_alt | ALT | Quantitative | |
| hosp_ggt | GGT | Quantitative | |
| hosp_bili | Bilirubin | Quantitative | |
| hosp_act | Coagulation | Quantitative | |
| hosp_sympt | Symptoms | Qualitative | Fever, diarrhoea, rash, fatigue, ulcers, among others |
| hosp_uci | Need for an Intensive Care Unit | Qualitative | Yes/No |
| hosp_vent | Need for mechanical ventilation | Qualitative | Yes/No |
| hosp_drugs | Drugs prescribed | Qualitative | ACT codes |
| hosp_doses | Drug doses | Quantitative | |
| hosp_tto_start | Treatment start date | Quantitative | MM/DD/YYYY: Up to 12/31/2024 |
| hosp_tto_end | Treatment end date | Quantitative | MM/DD/YYYY: Up to 12/31/2024 |
| hosp_drugs_cost | Cost of the drugs | Quantitative | In euros (€) |
| hosp_cost | Cost attributed to hospitalisation | Quantitative | In euros (€) |
| Hospital follow-up (I | MBDS) | | |
| followup | Number of follow-up visits after hospitalisation | Quantitative | |
| followup_dates | Dates of follow-up visits after hospitalisation | Quantitative | MM/DD/YYYY: Up to 12/31/2024 |
| followup_dx | Diagnosis made during the follow-up visits | Qualitative | ICD9 or ICD-10 |
| followup_hgb | Haemoglobin | Quantitative | |
| followup_plt | Platelets | Quantitative | |
| followup_wbc | Leucocytes | Quantitative | |
| followup_neut | Neutrophils | Quantitative | |

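### Treatment and hospital follow-up have no window after diagnosis, so Endpoint 10 misses primary-care treatment of people diagnosed late in the intervention year

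*SAP*

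**What the plan says.** **Detection.** SAP section 2.2 and the note under SAP Table 4 count detections over at least five years, up to the end of the intervention. The intervention lasts one year. SAP section 3.4 states that "the data for all the variables mentioned in Annex 1 will be collected after the year of intervention is completed". Neither document gives calendar dates for its start or end.

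**Treatment.** Objective 10 (SAP section 2.2) is "To measure the number of the diagnosed individuals that have received treatment". Endpoint 10 draws on both the primary-care record and the hospital dataset. In SAP Annex 1 the primary-care field `drugs` is defined as "Drugs prescribed to patients during the intervention". Protocol section 7, study variable 7, likewise restricts disease-related drugs to those "prescribed during the intervention period". The hospital fields `hosp_drugs` and `followup_drugs` carry no such restriction.

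**Dates.** Annex 1 gives the same limit, "MM/DD/YYYY: Up to 12/31/2024", for primary-care visits, treatment start and end, hospitalisation, and hospital follow-up visits.

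**Analysis.** SAP section 2.3 defines Endpoints 9 and 10 as numbers of patients, and Table 4 assigns both a bivariate analysis. Neither document sets a minimum follow-up, a window after diagnosis, a censoring rule or a time-to-event method. Section 2.2 labels Objectives 9 and 10 secondary; section 2.3 lists the matching endpoints as exploratory.

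**The concern.** A case detected in the first month of the intervention has about eleven months in which a primary-care prescription can be recorded; a case detected in the last month has less than one. A plain count treats both alike, so a person with no recorded treatment may be untreated or may have run out of observation time. For diagnoses made during the intervention, the error can only go one way: events are missed, never added.

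This matters because the hypothesis in Protocol section 2 is that detection improves health where effective care exists. Endpoints 9 and 10 are the trial's evidence that a detected case went on to receive care. An understated figure could be read as poor linkage to care when part of the shortfall comes from the calendar. The primary outcome and the individual-condition detection rates are not affected.

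There is a second gap. Objectives 9 and 10 do not restrict the diagnosed people to those found in the intervention year. For someone diagnosed earlier in the five-year span, the `drugs` field leaves out treatment given before the intervention began.

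**Working it through.** The documents give no expected treatment or follow-up proportion and no lag from diagnosis to either outcome. There is no planned figure to reproduce, and what follows is an illustration.

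**Inputs from the documents**
- Length of intervention: one year, T = 12 months (SAP sections 3.4 and 5.1).
- Detection closes at the end of the intervention (SAP section 2.2, note to Table 4).
- Capture of primary-care drugs closes at the same moment (SAP Annex 1; Protocol section 7, item 7).

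**Assumptions**
- Intervention-year diagnoses are spread evenly over the 12 months.
- Everyone eventually reaches the outcome.
- The lag is exponential with mean L; L = 1, 2, 3 and 6 months are tried.

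**Step 1: time available.** Mean time left after diagnosis is 12/2 = 6 months. A share of 3/12 = 25% of the year's cases have under 3 months, and 1/12 = 8% have under 1 month.

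**Step 2: share captured with the cut at the end of detection.** S = 1 − (L/T)(1 − e^(−T/L)).
- L = 1: 1 − (1/12)(1 − e^(−12)) = 0.917
- L = 2: 1 − (2/12)(1 − e^(−6)) = 0.834
- L = 3: 1 − (3/12)(1 − e^(−4)) = 0.755
- L = 6: 1 − (6/12)(1 − e^(−2)) = 0.568

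A fixed lag in place of an exponential one gives 1 − L/T: 92%, 83%, 75% and 50%.

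**Step 3: last-quarter diagnoses only.** Replacing T by 3 gives 68%, 48%, 37% and 21% for L = 1, 2, 3 and 6.

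**Step 4: hospital fields.** These stop at 12/31/2024, not at the end of the intervention. If the intervention ended W months before that date, S(W) = 1 − (L/T)[e^(−W/L) − e^(−(T+W)/L)].

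| Mean lag L (months) | W = 0 | W = 3 | W = 6 |
|---|---|---|---|
| 1 | 92% | 99.6% | about 100% |
| 2 | 83% | 96% | 99% |
| 3 | 75% | 91% | 97% |
| 6 | 57% | 74% | 84% |

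W is not stated. The first column applies to primary-care drugs whatever the calendar dates are. Which column applies to Endpoint 9 and to hospital treatment cannot be determined.

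**Step 5: cases diagnosed before the intervention year.** The 12-month model does not cover them. They lose treatment given before the `drugs` window opens, and the documents give nothing from which to size that loss.

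**The case against.** The strongest reply is that 12/31/2024 is only an extraction limit. No section says that the intervention ends on that day, so hospital visits and hospital drugs may already have months of extra time. Endpoint 10 also uses the hospital dataset, and the screening recommendations in the Protocol annexes send diagnosed people to the reference hospital's specialised unit. This part stands: it limits the firm conclusion to primary-care treatment and makes the rest conditional on W. It does not restore primary-care prescriptions written after the intervention closes.

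The reply is also right that the size rests on assumed lags. With a mean lag of 1 month the loss is 8%, which is minor, and only people diagnosed in the last weeks have almost no time; the average is 6 months.

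Three stronger readings are tempting but not supported:

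- **The comparison between arms is biased.** A reader might infer this because prompts stop once a test or diagnosis is recorded, which could bring diagnoses forward in intervention centres. A difference between arms needs a difference in diagnosis timing. That is possible, but nothing in the documents shows it. Objectives 9 and 10 are worded as measurement, not comparison, and Table 4 does not say by which factor the bivariate analysis is made.
- **Cure and death are cut off in the same way.** Neither is an objective or endpoint in SAP sections 2.2 and 2.3. The `cured` field has no date, window or definition, so no cut-off is documented for it.
- **Referral is cut off at the end of the intervention.** The Annex 1 definition can be read as limiting the diagnosis to the intervention period, not the referral.

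**Conclusion.** The point holds in a limited form. As written, the plan understates Endpoint 10, because capture of primary-care treatment closes at the moment detection closes and nothing adjusts for time since diagnosis. Endpoint 9 and hospital treatment are understated to the extent that the intervention ends near 12/31/2024. For cases from earlier years, the drug window also misses treatment given before the intervention.

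The direction is clear; the size is not known. Under even detection, an exponential lag and a cut at the end of detection, between 8% (mean lag 1 month) and 43% (mean lag 6 months) of the intervention year's eventual events would fall outside the data. These percentages illustrate a range and are not estimates for this trial. The endpoints concerned are listed as exploratory, so the consequence is a misleading linkage-to-care figure, not a threat to the main result. The repair is cheap enough to be worth making.

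**What to change.** In SAP Annex 1 and Table 4:

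1. State the calendar start and end of the intervention at each site.
2. Add a diagnosis date. Annex 1 lists the diagnosis fields as Yes/No with no date of their own, although monthly detection rates already require at least the month.
3. Redefine the treatment and hospital follow-up fields as events on or after the diagnosis date. State whether cases diagnosed before the intervention year are included. If they are, extend the drug field back to cover their window.
4. Report Endpoints 9 and 10 as the proportion of diagnosed people reaching the outcome within a fixed, pre-stated window, for example 6 months. This is a measurement window only and implies nothing about when care should be given.
5. Restrict the denominator to people with a full window before the data cut, or use time-to-event estimates censored at the cut. A later extract of these fields is optional.

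**Cost.** If data stop at the end of the intervention and detection is even, a 6-month full-window rule keeps (12 − 6)/12 = one half of the intervention-year cases. The time-to-event version keeps them all. A later extract would retain more cases but delays these endpoints and needs a second data pull. In Andalusia that pull would include repeat linkage to the hospital laboratory data and pseudo-anonymisation (SAP section 5.1). The primary outcome and the detection window are unchanged.
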